# **C2. Summary of Hematological TEAEs**

An overall summary of hematological TEAEs will summarize the number (%) of patients. Summaries of the following hematological TEAEs will be provided:

- All hematological TEAEs by preferred terms
- Hematological TEAEs grade 3 or higher by preferred terms
- Serious hematological TEAEs by preferred terms

Hematological TEAE preferred terms are Anemia, Leukopenia, White blood cell count decreased, Neutropenia, Neutrophil count decreased, Thrombocytopenia, Platelet count decreased, Lymphopenia, Lymphocyte count decreased, Haemoglobin decreased, Erythropenia, Red blood cell count decreased, Bone marrow failure, and Febrile neutropenia.

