1.4.3 Clinical Safety and Preliminary Efficacy for BGB-290-AU-002 and BGB-290-102 Phase 1 study

Clinical Safety and Preliminary Efficacy for BGB-290-AU-002 study

BGB-290-AU-002 is a FIH study evaluating pamiparib to characterize the safety, the MTD, preliminary anti-tumor activity, and the PK of pamiparib given as a monotherapy in a 3+3 dose escalation scheme. Pamiparib was administered in doses ranging from 2.5 mg orally (PO) BID up to 120 mg PO BID.

The study is being conducted in 3 Australian study centers, and preliminary data for 45 patients are available (cut-off date of 30 September 2016).

The preliminary safety data indicates the most frequent adverse events (AEs) ($\geq 10\%$ of patients) assessed as related to pamiparib were nausea (51%, n=23), fatigue (29%, n=13), vomiting (18%, n=8), diarrhea (16%, n=7), and decreased appetite (11%, n=5).

Hematologic AEs are of interest in this study. The most frequent hematologic AEs ($\geq 10\%$ of patients) assessed as related to pamiparib were anemia (22%, n=10) and neutropenia (11%, n=5). Hematologic AEs, regardless of relatedness, were reported in 40% of patients (n=18). Anemia was most frequent (33%, n=15), followed by neutropenia (11%, n=5) and thrombocytopenia (2%, n=1).

Twenty-six patients experienced Grade 3 AEs (regardless of relatedness), and no Grade 4 AEs were reported. Eleven Grade 3 AEs in 9 patients (20%) were considered related to pamiparib: anemia (11%, n=5), neutropenia (7%, n=3), hypophosphatemia (2%, n=1), paresthesia (2%, n=1), nausea (2%, n=1) and fatigue (2%, n=1).

Serious adverse events (SAEs) were reported in 25 patients, and for 3 patients they were considered related to pamiparib: anemia (n=2) and nausea (n=1). Three patients discontinued study drug because of an AE: vomiting (n=1), oral paresthesia (n=1), and right neck cutaneous metastases (n=1).

Four patients experienced a fatal $AE \le 28$ days after the last pamiparib dose. All deaths were due to complications of the underlying malignancy, and none was considered related to pamiparib.

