Four patients experienced AEs that were considered dose limiting toxicities (DLTs): 2 patients experienced Grade 2 nausea that persisted despite optimal standard medical therapy; 1 patient experienced Grade 2 anorexia and Grade 2 nausea, and 1 patient experienced Grade 2 nausea and Grade 2 paresthesia. Based on the encountered DLTs and the overall safety profile of pamiparib, the MTD of pamiparib was determined to be 80 mg PO BID (160 mg/day).

MDS or acute myeloid leukemia (AML) are recognized AEs in patients receiving PARP inhibitors (Ricks et al 2015). To date, no cases of either MDS or AML have been observed in any study that includes pamiparib.

Ten patients achieved either a complete (n=2) or partial (n=8) response; all responses were observed in patients with gynecological cancers.

Clinical Safety and Preliminary Efficacy for BGB-290-102 Phase 1 study

The Phase 1 portion of study BGB-290-102 evaluated the safety, tolerability, PK, and preliminary efficacy of pamiparib in Chinese patients with advanced high-grade, non-mucinous, epithelial ovarian cancer, including fallopian and primary peritoneal cancer, or TNBC. Three cohorts with BID dosing (20, 40, and 60 mg) were evaluated in the dose-escalation phase. Preliminary data for 15 patients are available (HGOC: n=9; TNBC: n=6; as of 25 September 2017): n=4 for 20 mg, n=4 for 40 mg and n=7 for 60 mg.

The most common related AEs were asthenia (n=12), nausea (n=12), decreased appetite (n=9), white blood cell count decreased (n=9), anemia (n=8) and neutrophil count decreased (n=7). Treatment-related Grade 3 AEs in \geq 2 patients were anemia (n=5), decreased neutrophil count and decreased white blood cell count (n=2 each). No \geq Grade 4 AEs were reported. All SAEs were not related to pamiparib (1 each of abdominal infection, ileus, and pleural effusion). No dose-limiting toxicities were reported; and the recommended Phase 2 dose was confirmed as 60 mg PO BID.

Available preliminary efficacy data for 8 HGOC patients (all platinum-resistant/refractory) showed 2 patients with partial response (on treatment: n=2; *BRCA1/2* mutation: n=1) and 4 with stable disease (on treatment: n=4; *BRCA1/2* mutation: n=2). Median duration of treatment for 9 HGOC patients was 133 days (range: 8–260). Available preliminary efficacy data for 5 TNBC patients showed progressive disease (PD) for all 5 (*BRCA1/2* mutation: n=1).

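### The pre/post-amendment TEAE tables in SAP 10.2 C2 count single preferred terms, so a cytopenia coded under two synonyms may be split and understated

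*SAP*

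**What the plan says.** SAP 6.7 proposes an ad hoc Phase 2 comparison of haematological safety. One subgroup is the patients whose first consent was under protocol version 5.0; the other is those who signed under at least one previous version. Appendix 10.2 sets it out in four parts: C1 laboratory values, C2 TEAEs, C3 exposure and dose modification, and C4 medications for anaemia.

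C2 names three tables: "All hematological TEAEs by preferred terms", "Hematological TEAEs grade 3 or higher by preferred terms" and "Serious hematological TEAEs by preferred terms". The terms that count are listed: "Hematological TEAE preferred terms are Anemia, Leukopenia, White blood cell count decreased, Neutropenia, Neutrophil count decreased, Thrombocytopenia, Platelet count decreased", followed by "Lymphopenia, Lymphocyte count decreased, Haemoglobin decreased, Erythropenia, Red blood cell count decreased, Bone marrow failure, and Febrile neutropenia". C2 also says: "An overall summary of hematological TEAEs will summarize the number (%) of patients". It does not say which rows that summary will have.

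Two rules in SAP 6.5.3 bear on this. Events are coded to the MedDRA lower-level term nearest to the investigator's own words. A patient with repeated events is counted once, at the highest grade, but only within one system organ class and preferred term.

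**The concern.** The purpose of C2 is to show whether haematological toxicity differed between the two periods. A reader will want the proportion of patients with any neutropenia, any thrombocytopenia and so on, before and after. The tables as specified give no such row. They give one row per synonym, and which row a patient falls into depends on how the investigator worded the event.

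Two things are at stake if both synonyms are used. Each row would understate the cytopenia, and the rows could not be added afterwards, because one patient may carry both terms. A change in reporting habit between periods would also appear in the rows as a change in toxicity.

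**Working it through.** The plan states no incidence, sample size or power for C2, so there is no figure to reproduce. The check is of the text, followed by a bound on the size.

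**Step 1. Does the list hold synonyms?** Arranged by lineage, the C2 terms are:

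| Lineage | Terms on the C2 list |
|---|---|
| Neutrophils | Neutropenia; Neutrophil count decreased |
| Platelets | Thrombocytopenia; Platelet count decreased |
| White cells | Leukopenia; White blood cell count decreased |
| Lymphocytes | Lymphopenia; Lymphocyte count decreased |
| Red cells | Anemia; Haemoglobin decreased; also Erythropenia; Red blood cell count decreased |
| Not a synonym of one count | Febrile neutropenia; Bone marrow failure |

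The protocol treats the name and the low count as one toxicity. The haematology footnote to protocol Table 7 defines neutropenia by the neutrophil count and thrombocytopenia by platelets. Protocol Table 9 defines anaemia by haemoglobin.

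**Step 2. Does any rule bring synonyms together?** SAP 6.5.3 does not, since it removes duplicates only within a preferred term. C2 does not define a group. C4, in the same appendix and for the same comparison, does group drug terms under two headings (erythropoietin and red-cell transfusion).

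**Step 3. Bound on the size.** For one pair of synonyms A and B, let p be the true proportion of patients with the cytopenia. Among them, let a be the share with A only, b the share with both and c the share with B only, so a + b + c = 1. Then:

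- row A = p(a + b) and row B = p(b + c)
- grouped row = p
- larger row ≤ p ≤ row A + row B, and the sum of the rows exceeds p by p × b

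Illustration with p = 40%. Every rate and split here is an assumption.

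| Split of affected patients | Row A | Row B | Sum | Grouped row |
|---|---|---|---|---|
| All A | 40% | 0% | 40% | 40% |
| 90% A, 10% B | 36% | 4% | 40% | 40% |
| 70% A, 30% B | 28% | 12% | 40% | 40% |
| 50% A, 50% B | 20% | 20% | 40% | 40% |
| 40% A only, 20% both, 40% B only | 24% | 24% | 48% | 40% |

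The larger row therefore loses between 0 and one half of the true incidence. The last line shows why the rows cannot simply be added: 24% + 24% = 48%, against a true 40%.

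**Step 4. Effect on the comparison (assumed rates).**

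- *Same coding habit in both periods.* A true 60% against 40% is a 20-point difference. With 90%, 70% or 50% coded to A and no overlap, row A shows 54% against 36%, 42% against 28%, or 30% against 20%. The differences are 18, 14 and 10 points.
- *Different habit by period.* Take a true 40% in both periods, with 80% coded to A before and 50% after. Row A shows 0.40 × 0.80 = 32% against 0.40 × 0.50 = 20%. This is a 12-point difference with no change in toxicity.

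**Step 5. What do the documents show about wording in this trial?** Protocol 1.4.3 reports, for Phase 1 of this study, "white blood cell count decreased (n=9), anemia (n=8) and neutrophil count decreased (n=7"). The entry "neutropenia (11%, n=5") in the same section belongs to BGB-290-AU-002. Within this study's summary, each lineage has one wording.

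**The case against.** The strongest reply is that nothing in the documents shows a split will occur. A reader might take the two wordings in protocol 1.4.3 as proof of mixed coding, but they come from two different studies. The summary of 15 Phase 1 patients in this trial points towards one term per lineage, and hence towards no loss. It does not settle what happens in Phase 2. Nor do the documents say that wording changed with version 5.0.

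A reader might also infer that the anaemia comparison is the one most at risk, since the amendment revised the anaemia rules. The documents point the other way: both studies report anaemia under that name, and neither summary mentions decreased haemoglobin. Anaemia looks the least exposed lineage.

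A third tempting inference is that the whole pre/post comparison is distorted. It is not. C1 compares abnormal values, and shifts of two or more toxicity grades, by laboratory parameter. These do not depend on adverse event wording, so they could expose an artefact of coding. C4 compares grouped anaemia treatments. C1 does not, however, count Grade 3 or higher TEAEs or serious TEAEs, so for those it does not fill the gap.

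Finally, SAP 10.3 refers to a separate programming document that is not available here and might define groups. That possibility stands, but C2 itself specifies tabulation by preferred term.

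**Conclusion.** The point holds for C2, as a conditional one. The three TEAE tables are by single preferred term, the list holds synonyms for each cell line, and no rule in the SAP combines them. If both synonyms of a pair occur in the Phase 2 data, the cytopenia may be split and its incidence understated, and a shift of wording between periods could pass for a change in toxicity.

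The size is unknown. For a two-term pair the larger row loses from zero to one half of the true incidence, and it loses nothing for a lineage coded to one term. The documents do not support saying that each cytopenia is in fact understated. The consequence is limited: the comparison is ad hoc, descriptive and non-randomised, with no test specified, and ORR is unaffected. This is an inexpensive improvement, not a flaw in the main analysis.

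**What to change.** In C2, for all three tables:

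- Add one grouped row per lineage (anaemia, neutropenia, leukopenia, thrombocytopenia, lymphopenia), each with a listed set of preferred terms. The list should settle where Erythropenia and Red blood cell count decreased belong.
- Count each patient once per group, at the worst grade.
- Keep the preferred-term rows beneath each group.
- State in advance whether Febrile neutropenia and Bone marrow failure stay separate.
- Compare the pre- and post-amendment subgroups on the grouped rows.

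The cost is a grouping list and a few extra rows in tables already planned. No new data are needed.

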# C3. Extent of Exposure and Dose Modification

The following measures of overall extent of study drug exposure in patients between pre- and post-PA will be summarized:

• Duration of treatment (months), defined as (earlier of date of last nonzero dose and data cutoff date – date of first dose + 1) / 30.4375

**Version 1.1**: 02/28/2020 Page 27 of 28

- Number (%) of patients in each treatment duration category
- Number (%) of patients with dose modification (interruption and reduction)
- Number (%) of patients with dose interruptions and reasons of dose interruptions
- Number (%) of patients with dose reductions and reasons of dose reductions
- Time to first dose reduction (weeks), defined as (earlier of date of first nonzero dose date date of first dose + 1) / 30.4375 for patients with dose reduction

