#### 6.2 DATA ANALYSIS GENERAL CONSIDERATIONS

#### **6.2.1** Definitions and Computations

Study day: Study day will be calculated in reference to the date of the first dose of study drug. For assessments conducted on or after the date of the first dose of study drug, study day will be calculated as (assessment date – date of first dose of study drug + 1). For assessments conducted before the date of the first dose of study drug, study day is calculated as (assessment date – date of first dose of study drug). There is no study day 0.

In the situation where the event date is partial or missing, the date will appear partial or missing in the listings. Study day and any corresponding durations will be presented based on the imputations specified in Appendix 10.1.

Treatment duration: The treatment duration will be calculated as (date of the last non-zero dose of study drug - date of first dose of study drug + 1).

Baseline: the non-missing value most recently collected before the first dose.

All calculations and analyses will be conducted using SAS version 9.4 or higher.

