# 6.2.2 Conventions

Unless otherwise specified, the following conventions will be applied to all analyses:

- 1 year = 365.25 days. Number of years is calculated as (days/365.25) rounded up to 1 significant digit.
- 1 month = 30.4375 days. Number of months is calculated as (days/30.4375) rounded up to 1 significant digit.
- Age will be calculated as the integer part of (date of informed consent date of birth + 1)/365.25
- P-values will be rounded to 4 decimal places. P-values that round to 0.0000 will be presented as '< 0.0001' and p-values that round to 1.000 will be presented as '> 0.9999'.
- Time-to-event or duration of event endpoints will be based on the actual date the radiograph was obtained rather than the associated visit date.
- Missing efficacy or safety data will not be imputed unless otherwise specified.
- For laboratory results collected as < or >, a numeric value, 0.0000000001 will be subtracted or added, respectively, to the value.
- For by-visit observed data analyses, percentages will be calculated based on the number of patients with non-missing data as the denominator, unless otherwise specified.

**Version 1.1**: 02/28/2020 Page 11 of 28

• For continuous endpoints, summary statistics will include n, mean, standard deviation, median, Q1, Q3 and range (minimum and maximum).

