# 6.5.2 Extent of Exposure

The number (and percentage) of patients requiring dose reductions, dose interruption, and treatment discontinuation will be summarized. One cycle is defined as 21 days of treatment except for the first cycle in the Phase 1 portion of this study.

The duration of treatment (months) will be summarized with descriptive statistics. It will be calculated as (Date of last non-zero dose – Date of first dose + 1) / 30.4375.

Number of patients with dose reductions and treatment discontinuation and their reasons, as well as number of patients with any dose modification will be summarized by counts and percentages according to study medication data. In addition, frequency of dose reductions and dose interruption will be summarized by categories  $(0, 1, \ge 2)$ .

Average dose intensity per patient (in mg/day) and relative dose intensity (total dose received / total dose planned) per patient will be summarized. Average dose intensity is calculated as the total dose (mg) taken by a patient divided by overall duration of exposure (= Date of last non-zero dose – Date of first dose + 1) for individual patient. Relative dose intensity is calculated as the total dose (mg) taken by a patient divided by the total dose planned for the patient by study design. To note, for the Phase 1 portion of the study, the planned dose for a patient will be a single dose on day 1 at a given dose level, no dose on day 2 and then twice daily for the next 21 days for Cycle 1; and then twice-daily for later treatment cycles. Patients in the Phase 2 portion of the study will always be treated on twice-daily administration at the prescribed dose level.

Patient data listings will be provided for all dosing records.

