#### 6.7 AD HOC ANALYSES

Protocol version 5.0 was released on 21 September 2018, which was in the middle of study conduct. The new version of the protocol was mainly aiming to provide more proactive dose modification algorithm and closer hematology monitoring in early stage of drug administration in order to improve the hematological safety management.

The analysis of hematological safety data comparison of pamiparib between pre- and post-protocol amendment (PA) for patients in phase 2 is proposed. Post-PA subgroup is defined as patients signed the first ICF under protocol version 5.0 and Pre-PA subgroup includes patients who signed ICF under at least one previous protocol version. The detailed description of the analysis is in Appendix 10.2.

As a consequence of dose reduction, a proportion of patients will end up with lower dose levels, other than the starting dose level, for their rest of treatment. An analysis of ORR, DCR, CBR, TTR, DOR and PFS will be summarized by most recent prescribed dose level (60mg, 40mg and 20mg) by IRC for PSOC patients in phase 2.

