# IMPUTATION FOR MEDICATIONS/THERAPIES/PROCEDURES WITH MISSING OR PARTIAL DATES

When the start date or end date of a medication/therapy/procedure is partially missing, the date will be imputed to determine whether the medication/therapy/procedure is prior or concomitant. The following rules will be applied to impute partial dates for medication/therapy/procedure:

If start date of a medication/therapy/procedure is partially missing, impute as follows:

- If both month and day are missing, then set to January 01
- If only day is missing, then set to the first of the month
- If the imputed start date > death date, then set to death date

If end date of a medication/therapy/procedure is partially missing, impute as follows:

- If both month and day are missing, then set to December 31
- If only day is missing, then set to last day of the month
- If the imputed end date > death date, then set to death date

Version 1.1: 02/28/2020 Page 26 of 28

• For prior anticancer therapy, the imputed end date should be the first dose date – 15 at the latest after imputation.

If the year of start date or year of end date of a medication/therapy/procedure is missing, or the start date or end date is completely missing, do not impute.

For detailed imputation rule for new anti-cancer therapy and death date, etc., please refer to a separate document "Standard Definitions and Derivation Rules of Key Variables V1".

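### SAP Appendix 10.2 C3: the formula for time to first dose reduction contains no dose-reduction date and divides by days per month under a label of weeks

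*SAP*

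**What the plan says.** SAP 6.7 plans an ad hoc comparison of hematological safety in Phase 2 patients who consented before version 5.0 of the protocol (Pre-PA) with those who first consented under it (Post-PA). It describes version 5.0 as aiming at a "more proactive dose modification algorithm and closer hematology monitoring in early stage of drug administration". Appendix 10.2 C3 lists the exposure measures for this comparison. The last one is "Time to first dose reduction (weeks), defined as (earlier of date of first nonzero dose date date of first dose + 1) / 30.4375", restricted to patients with a dose reduction.

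The first measure in the same list reads "Duration of treatment (months), defined as (earlier of date of last nonzero dose and data cutoff date", followed by minus the first dose date, plus 1, over 30.4375. SAP 6.5.2 uses the same divisor, again for months: "The duration of treatment (months) will be summarized with descriptive statistics". SAP 6.2.2 fixes its meaning: "1 month = 30.4375 days".

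Neither document gives any other definition of time to first dose reduction. For some derivations and for programming rules, SAP Appendices 10.1 and 10.3 send the reader elsewhere ("please refer to a separate document"); that document was not available for this review.

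**The concern.** The formula does not measure what its name says. It uses two dates, that of the first nonzero dose and that of the first dose, and neither says when the dose was lowered. The words *earlier of* call for two candidate dates, as in the duration measure, but only one follows. Separately, a quantity labelled in weeks is divided by the number of days in a month. The line looks like the duration formula carried over and only partly edited.

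At stake is the only C3 measure of when reductions happened; the other reduction items are counts and reasons. Timing matters here because the amendment was directed at the early part of treatment. Followed literally, the measure cannot show any Pre-PA versus Post-PA difference. A half-correction may be worse than none: a constant is easily noticed in the output, whereas months presented as weeks look plausible.

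**Working it through.** The plan states no numerical result for this measure, so there is no figure to reproduce. The check evaluates the rule itself.

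**Inputs**
- Formula, label and population: SAP Appendix 10.2 C3.
- Divisor: 30.4375 days per month (SAP 6.2.2), consistent with that section's 365.25 days per year, since 365.25/12 = 30.4375.
- Minus sign between the two dates: taken from the parallel duration measure in C3. Its absence is treated as a PDF-reading loss, not as an error in the plan.
- First nonzero dose date = first dose date: twice-daily dosing in Phase 2 starts on Cycle 1 Day 1 (protocol Table 7, footnote 19).

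**Step 1. The rule taken literally**

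(first nonzero dose date − first dose date + 1)/30.4375 = (0 + 1)/30.4375 = 0.033 for every patient with a reduction.

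**Step 2. Correct the divisor only**

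(0 + 1)/7 = 0.143. Still a constant, so changing the divisor does not cure the missing date.

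**Step 3. Correct the date only**

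For a first reduction on study day *d*, the numerator is *d*. The result is *d*/30.4375 where *d*/7 is needed. The ratio is 30.4375/7 = 4.35 for every *d*.

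| Study day of first reduction | *d*/30.4375 (labelled weeks) | *d*/7 (true weeks) |
|---|---|---|
| 8 | 0.26 | 1.14 |
| 22 (Cycle 2 Day 1) | 0.72 | 3.14 |
| 43 (Cycle 3 Day 1) | 1.41 | 6.14 |
| 63 (last day of Cycle 3, 3 × 21) | 2.07 | 9.00 |

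The days are illustrations; the documents give no distribution of reduction dates. Days 22 and 43 are visit days in protocol Table 7. Day 63 ends the three cycles for which footnote 9 of that table requires weekly hematology.

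**Step 4. What depends on the reconstruction**

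The value 0.033 needs the restored minus sign and the coincidence of the two dates. The unit mismatch and the factor 4.35 need neither. The missing reduction date is visible in the text, however the sign is read. The rounding convention in SAP 6.2.2 may alter how 0.033 is displayed, but not that it is the same for everyone.

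**The case against.** The line is visibly damaged in the text supplied: no operator stands between the two dates, so strictly nothing can be computed until one is inserted, and more than a dash may have been lost. On that view the fair statement is that the formula is incomplete, and 0.033 belongs to a reconstruction. This stands as a caution on the constant. It does not explain the month divisor under a weeks label, and a lost dash does not explain the absent reduction date.

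The harm is also hypothetical. The name makes the intent plain, a constant would be caught in the first output, and the separate derivation document may already be right. All true, and the reason to treat this as an erratum. But the SAP states an explicit formula in what it calls an a priori plan. If the other document differs, the two conflict; if it does not cover this ad hoc variable, the SAP line is the only rule.

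Finally, the unit could be reconciled the other way, by keeping 30.4375 and relabelling as months, and the date of first dose reduction itself needs a definition, because many reductions in protocol Table 9 follow a hold. Both points are fair and bear on the wording of the correction. Neither defends the present text.

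**Conclusion.** The concern holds. The rule has two independent errors, and both need correcting: no dose-reduction date, and a month divisor for a measure in weeks. Read with the minus sign restored and the first dose taken as nonzero, it returns 0.033 for every patient with a reduction. With the date alone repaired, it understates time in weeks by a factor of 4.35.

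The consequence is confined to one descriptive ad hoc measure with no test attached. That measure covers only patients who had a reduction, so it depends on length of follow-up even when correctly defined. The C3 numbers and reasons for reductions and interruptions, the main safety tables and the primary response-rate analysis do not use it. Whether any output would be wrong cannot be judged without the separate derivation document; the SAP text is wrong either way. It should be corrected, as a text erratum.

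**What to change.** Replace the definition in Appendix 10.2 C3 with: time to first dose reduction (weeks) = (date of first dose reduction − date of first dose + 1)/7, in patients with a dose reduction, as already planned. This keeps the stated unit and extends the SAP's own day count to a dosing event; SAP 6.2.1 sets that count for assessments ("For assessments conducted on or after the date of the first dose of study drug, study day will be calculated as (assessment date", minus the first dose date, plus 1). State in the same line which dosing record supplies the reduction date when the reduction follows a hold. Then confirm that the separate derivation document carries the same date and divisor.

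The cost is one line of SAP text and a check of one derivation. No new data are needed: SAP 6.5.2 already summarizes reductions from the study medication data, and "Patient data listings will be provided for all dosing records".
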